## 3.2 Omadacycline

The investigational product, omadacycline (formerly named PTK 0796), is the first member of the aminomethylcycline class of antibiotics, which are semisynthetic derivatives of the tetracycline class. As a class, the tetracyclines have been in use for approximately 70 years. They are well-tolerated and have proven effective in the treatment of a variety of bacterial infections. NUZYRATM (omadacycline) has been approved by the US Food and Drug Administration (FDA) for the treatment of adult patients with CABP caused by susceptible microorganisms.

Omadacycline has demonstrated activity against the most common CABP pathogens, including isolates resistant to older antibiotics. This study is intended to evaluate the safety and efficacy of intravenous (iv) and oral (po) omadacycline as compared to iv and po moxifloxacin in the treatment of pneumonia patient outcomes research team (PORT) Risk Class III and IV adults with CABP.

Please refer to the current version of the Investigator's Brochure or the NUZYRATM (omadacycline) United States Prescribing Information (USPI) for additional information on omadacycline.

## **4 STUDY OBJECTIVES**

### 4.1 **Primary Objective**

The primary objective of this study is:

• To demonstrate that iv to po omadacycline is non-inferior to iv to po moxifloxacin in the treatment of adults with PORT Risk Class III and IV CABP.

### 4.2 Secondary Objectives

The secondary objectives of this study are:

- To evaluate the safety of omadacycline in the treatment of adults with CABP in the Safety population.
- To evaluate the Clinical Response according to the identified causative pathogen.
- To evaluate the pharmacokinetics (PK) of omadacycline in adults with CABP.

# **5** INVESTIGATIONAL PLAN

## 5.1 Overall Study Description

This is a randomized (1:1), active comparator controlled, double-blind, Phase 3 study comparing omadacycline and moxifloxacin in the treatment of adults with CABP (PORT Risk Class III and IV). Both iv and po phases of the study will be double-blind.

Subjects will participate in the study for up to 37 days. Following a Screening period of up to 24 hours, eligible subjects will be randomized to receive treatment. Subject randomization will be stratified by PORT Risk Class (III or IV), and by receipt of an allowed antibacterial therapy (see Appendix 4) in the 72 hours prior to study treatment.

Eligible subjects with a PORT RISK Class III or IV will be randomized to receive 7 to 10 days of iv treatment with the option to switch to po treatment on Day 3. Subjects with bacteremia identified at Screening can receive up to 14 days of treatment. Switch to po will NOT be permitted until after the subject has completed at least 2 days of iv treatment. The decision to switch to po treatment will be made by the investigator; the subject should be considered clinically stable and meet all criteria for transition to a po regimen. Specifically, the subject must meet the following requirements and this should be noted in source documents and recorded on the electronic case report form (eCRF):

- Temperature  $\leq 37.8^{\circ}C (100^{\circ}F)$
- Heart rate  $\leq 100$  beats/minute
- Respiratory rate (RR)  $\leq$  24 breaths/minute
- Systolic blood pressure (SBP)  $\ge$  90 mm Hg
- Oxygen saturation ≥ 90% as measured by pulse oximetry or partial pressure of arterial oxygen (PaO2) ≥ 60 mm Hg by arterial blood gas (ABG)
- Normal ("absence of confusion") or return to baseline mental status
- Ability to maintain po intake.

		Study Day	Study Day	Study Days
Group	Test Article	1	2	3 to 10 a
1	Omadacycline	200 mg iv QD or 100 mg iv BID	100 mg iv	100 mg iv or 300 mg po
2	Moxifloxacin	400 mg iv	400 mg iv	400 mg iv or 400 mg po

Eligible subjects will be randomized to one of the following treatment groups:

BID = twice a day dosing, iv = intravenous, po = per oral, PORT = pneumonia patient outcomes research team, QD = once a day dosing.

The total duration of treatment for subjects is 7-10 days, with up to 14 days of treatment for subjects with bacteremia.

Subjects will return to the study site for a Post Therapy Evaluation (PTE) 5 to 10 days after the last dose of test article. A Final Follow-up visit (Final Follow-up) will be conducted within 30 to 37 days following the first dose of test article. The Final Follow-up assessment may be conducted via telephone contact or by another interactive technology for subjects who were considered to be Clinical Success in the opinion of the investigator at end of treatment (EOT) and PTE and had no adverse events (AEs) or clinically significant laboratory or electrocardiogram (ECG) abnormalities noted at or after the PTE visit.

Otherwise, this assessment is to be performed with an in-person study visit.

Refer to the Schedule of Events (Appendix 1) for a complete summary of subject visits and assessments.

## 5.2 Rationale for Study Design

The study was designed in accordance with the FDA  and European Medicines Agency (EMA) guidance on developing antimicrobial drugs for the treatment of CABP, in addition to the guidelines created jointly by the Infectious Diseases Society of America and the American Thoracic Society.

## 5.3 Rationale for Control Group

Moxifloxacin (400 mg iv every 24 hours [q24h] with the option to transition to 400 mg po q24h) was chosen as the comparator given the wide acceptance of fluoroquinolone monotherapy as a safe, first-line option for treating subjects with CABP. Moxifloxacin provides a broad spectrum of activity against respiratory pathogens that are causative agents of CABP, including typical (eg, *Streptococcus pneumoniae*) and atypical (eg, *Legionella, Chlamydophila*, and *Mycoplasma* spp.) pathogens, with a similar spectrum of activity to that of omadacycline. Like omadacycline, moxifloxacin has both iv and po formulation options and is administered once daily.

## 5.4 Approximate Duration of Subject Participation

Subjects will participate in the study for up to 37 days. Eligible subjects will be randomly assigned to receive to 7 to 10 days of iv/po treatment of either omadacycline or moxifloxacin. Subjects with bacteremia confirmed from local blood culture drawn at Screening can receive up to 14 days of treatment. Subjects will return to the site for an EOT visit on the day of or within 2 days following the last dose of test article. Subjects will return to the study site for a PTE 5 to 10 days after the last dose of test article. A Final Follow-up assessment will be conducted within 30 to 37 days following the first dose of test article.

## 5.5 Approximate Duration of Study

The study is expected to be clinically complete in approximately 24 months.

## 5.6 Approximate Number of Subjects

Approximately 670 subjects will be enrolled at approximately 75 sites globally.

# **6 STUDY POPULATION SELECTION**

Each subject must participate in the informed consent process and sign and date an IRB/IEC/REB approved informed consent form (ICF) before any procedures specified in this protocol are performed.

### 6.1 Study Population

Approximately 670 patients will be enrolled at approximately 75 sites globally. Subjects will be randomized in a 1:1 ratio.

## 6.2 Inclusion Criteria

Each subject must meet all of the following criteria to be enrolled in this study:

- 1. Written and signed informed consent must be obtained before any protocol specific assessment is performed.
- 2. Male or female, aged 18 years or older.
- 3. Has at least 3 of the following symptoms:
  - Cough
  - Production of purulent sputum
  - Dyspnea (shortness of breath)
  - Pleuritic chest pain
- 4. Has at least TWO of the following abnormal vital signs:
  - Fever or hypothermia documented by the investigator (temperature > 38.0°C [100.4°F] or < 36.0°C [95.5°F])
  - Hypotension with SBP < 90 mm Hg
  - Heart rate > 90 beats per minute (bpm)
  - RR > 20 breaths/minute
- 5. Has at least 1 clinical sign or laboratory finding associated with CABP:
  - Hypoxemia ( $PaO_2 < 60 \text{ mm Hg by ABG or oxygen saturation} < 90\%$  by pulse oximetry)
  - Physical examination findings of pulmonary consolidation (eg, dullness on percussion, bronchial breath sounds, or egophony)
  - An elevated total white blood cell (WBC) count (> 12,000 cells/mm^3) or leucopenia (WBC < 4,000 cells/mm^3) or elevated immature neutrophils (> 15% band forms) (regardless of total peripheral WBC count)
- 6. Has disease categorized as being PORT Risk Class III or IV at Screening (see PORT Risk Class calculation in Appendix 5).
- 7. Radiographically-confirmed pneumonia, ie, new or progressive pulmonary infiltrate(s) on chest X-ray (CXR) or chest computed tomography (CT) scan consistent with acute bacterial pneumonia within 48 hours prior to the first dose of test article.

- 8. Is expected to require a minimum of at least 2 days of iv therapy for the initial treatment of CABP.
- 9. Females must have a negative pregnancy test at Screening and agree to comply with using an acceptable method of birth control as per your local requirements (eg, abstinence, po contraceptive, intrauterine device [IUD], barrier contraception [condom], tubal ligation, hysterectomy, bilateral oophorectomy, postmenopausal or vasectomized partner) from Screening through PTE. Males must agree to use an acceptable method of birth control with female partner(s) and must not donate sperm from Screening through PTE.

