### 8.13.2 Clinical Stability

The formal determination of the subject's Clinical Stability will be done programmatically using the investigator's assessment of the subject's vital signs entered into the eCRF. The investigator is not responsible for categorizing the subject's Clinical Stability. Clinical Stability will be assessed daily and analyzed by day, ECR window, EOT, and PTE.

Patients will be considered clinically stable if they achieved all of the following criteria:

- Temperature  $\leq 37.8^{\circ}C (100^{\circ}F);$
- Heart Rate  $\leq 100$  beats/minute;
- $RR \le 24$  breaths/minute;
- SBP  $\geq$  90 mmHg; and
- Arterial Oxygen Saturation  $\ge 90\%$  or  $PaO_2 \ge 60$  mmHg on room air.

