## 12.8 Analysis of Additional Efficacy Variables

Additional efficacy analyses will be conducted to support the efficacy findings of the primary and secondary outcomes. CIs will be determined for descriptive purposes, but no conclusions of NI will be made.

The number and percentage of subjects classified as a Clinical Success, Clinical Failure and Indeterminate by the Investigator's Assessment at EOT in the ITT and CE populations (by definition, subjects with an Indeterminate response are excluded from the CE population) will be calculated. A 2-sided unadjusted 95% CI will be constructed for the observed difference in the Clinical Success rate using the method of Miettinen and Nurminen.

The number and percentage of subjects with stabilization of vital signs and clinical signs/laboratory findings associated with CABP at 72-120 hours post first dose of test article will be presented by treatment group in the ITT population. These include body temperature (no fever or hypothermia), SBP (> 90 mm Hg), heart rate (< 90 bpm), RR (< 20 breaths/minute), PaO2 ( $\geq$  60 mm Hg by ABG or oxygen saturation  $\geq$  90% by pulse oximetry), physical exam findings (no findings of pulmonary consolidation), WBC count (< 12,000 cells/mm3 or  $\geq$  4,000 cells/mm3) or immature neutrophils (< 15%).

A summary (number and percentage of subjects) of the assessment of clinical signs and symptoms of CABP at each time point throughout the study will be presented by treatment group in the ITT population. The number and percentage of subjects with resolution of signs and symptoms present at Screening (back to pre-CABP status) will also be provided by study visit. The number and percentage of subjects with no worsening of clinical symptoms of CABP and with the absence of new symptoms of CABP will also be provided by treatment group in the ITT population.

The per-subject and per-pathogen microbiologic outcomes will be provided for the microITT and ME populations at the EOT and PTE visits. Two-sided unadjusted 95% CIs will be provided for the difference in per-subject microbiological favorable outcome rates.

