9.4 Additional Analyses

Additional efficacy analyses will be conducted to support the efficacy findings of the primary and secondary outcomes. CIs will be determined for descriptive purposes, but no conclusions of NI will be made.

Clinical Outcomes

The number and percentage of subjects classified as a Clinical Success, Clinical Failure, and Indeterminate by the Investigator's Assessment at EOT in the ITT and CE-EOT populations (by definition subjects with an Indeterminate response are excluded from the CE-EOT population) will be calculated. The number and percentage of subjects in each response category for the assessment of Clinical response at PTE (based on the investigator's assessment) in the microITT population will also be provided. Two-sided unadjusted 95% CIs will be constructed for the observed difference in the Clinical Success rate using the method of Miettinen and Nurminen (1985).

The number and percentage of subjects with stabilization of all vital signs associated with CABP at 72 to 120 hours post first dose of test article will be presented by treatment group in the ITT population as will the number and percentage of subjects with stabilization of each vital sign. These include temperature (no fever or hypothermia), SBP (> 90 mmHg), heart rate (< 90 bpm), RR (< 20 breaths/minutes), and PaO₂ (> 60 mmHg by pulse oximetry or ABG). WBC count (< 12,000 cells/mm³ or \geq 4,000 cells/mm³) and immature neutrophils (< 15%).

A summary (number and percentage of subjects) of the assessment of clinical symptoms of CABP at each time point throughout the study will be presented by treatment group in the ITT population. Clinical symptoms of CABP (cough, pleuritic chest pain, dyspnea, and phlegm/sputum production) will be summarized as shift tables of score (absent, mild, moderate, and severe) as compared with baseline. Percentages for clinical symptoms will be based on the number of subjects with a baseline and post-baseline evaluation at the time point of the specific clinical symptom. The number and percentage of subjects with resolution of all symptoms present at baseline (back to pre-CABP status) will also be provided by study visit in the ITT population. The number and percentage of subjects with no worsening of clinical symptoms of CABP and with the absence of new symptoms of CABP will also be provided by treatment group and study visit in the ITT population.

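### The per-sign 'stabilization' percentages at 72–120 h count ITT subjects whose sign was never abnormal, which shrinks per-sign arm differences in a descriptive table

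*Protocol*

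**What the plan says.** **Entry.** Criterion 4 of Protocol 6.2 is "Has at least TWO of the following abnormal vital signs": temperature, systolic pressure (SBP), heart rate and respiratory rate. Criterion 5 asks for one of three: hypoxemia, consolidation on examination, or an abnormal white cell or band count.

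**Analysis.** Protocol 12.8 presents, by arm in the ITT population, the subjects "with stabilization of vital signs and clinical signs/laboratory findings associated with CABP at 72-120 hours post first dose of test article". SAP 9.4 first presents stabilization of all vital signs together. It then adds the single signs: "in the ITT population as will the number and percentage of subjects with stabilization of each vital sign".

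**Definition.** The SAP gives limits and nothing more: "These include temperature (no fever or hypothermia), SBP (> 90 mmHg), heart rate (< 90 bpm), RR (< 20 breaths/minutes", followed by limits for oxygenation, white cells and bands. Neither document requires the sign to have been abnormal at baseline. Under SAP 7.3 only subjects with missing values leave the denominator.

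**Contrast in the same section.** For symptoms, SAP 9.4 ties the event to entry status: "The number and percentage of subjects with resolution of all symptoms present at baseline". It also plans symptom shift tables against baseline. No such cross-tabulation is planned for vital signs.

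**The concern.** Stabilization, in ordinary use, means that something abnormal has settled. In the per-sign rows, a subject who never had the abnormality is counted as having recovered from it, provided the value is still within limits at 72–120 h. Each percentage therefore mixes recovery in subjects abnormal at entry with persistence of normality in the rest.

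The mixing pulls the arms together. In a non-inferiority trial that direction flatters the conclusion, and SAP 9.4 offers these analyses as support for the primary and secondary findings. A reader of the per-sign rows cannot tell how many subjects with, say, tachypnea at entry had recovered in each arm.

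**Working it through.** The plan states no rate for any stabilization measure, so there is no figure of its own to reproduce. Its sample size is used for scale only: 670 subjects at 1:1, or 335 per arm.

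**1. What the entry rule fixes.** Each eligible subject has at least two of four vital signs abnormal, so the four shares q add to at least 200% and average at least 50%. A single sign can have any q. If SBP < 90 mmHg had q = 5%, the other three would average at least (200 − 5)/3 = 65%. For the three criterion 5 findings, one is enough, so their shares add to at least 100% and average at least one third.

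**2. Formula.** Let r be the rate within limits at 72–120 h among subjects abnormal at entry, and s the rate among subjects normal at entry.

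ITT rate in an arm = q × r + (1 − q) × s

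If q and s are the same in both arms, the ITT difference = q × (r₁ − r₂) = q × D.

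**3. Numbers.** The documents give none of q, r or s. Assumed: r = 60% against 70% (D = −10 points) and s = 95% in both arms. At q = 50%, for example, 0.5 × 60 + 0.5 × 95 = 77.5% against 0.5 × 70 + 0.5 × 95 = 82.5%. Intervals are Wald 95%, in points.

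| q | ITT rates (%) | ITT difference (95% CI) | Abnormal at entry only: difference (95% CI) | n per arm, abnormal at entry |
|---|---|---|---|---|
| 5% | 93.25 vs 93.75 | −0.5 (−4.2 to 3.2) | −10.0 (−42.1 to 22.1) | 17 |
| 25% | 86.25 vs 88.75 | −2.5 (−7.5 to 2.5) | −10.0 (−24.4 to 4.4) | 84 |
| 50% | 77.5 vs 82.5 | −5.0 (−11.0 to 1.0) | −10.0 (−20.2 to 0.2) | 168 |
| 75% | 68.75 vs 76.25 | −7.5 (−14.2 to −0.8) | −10.0 (−18.3 to −1.7) | 251 |
| 100% | 60 vs 70 | −10.0 (−17.2 to −2.8) | −10.0 (−17.2 to −2.8) | 335 |

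**4. Evidence lost.** The difference shrinks more than the evidence does. At q = 50%, the difference divided by its standard error is about 1.6 in ITT (5.0/3.08) and 1.9 in the restricted set (10.0/5.18).

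**5. The composite.** To be stable on all vital signs in SAP 9.4, a subject needs heart rate < 90, respiratory rate < 20, SBP > 90 and no fever or hypothermia. Criterion 4 requires at least two of these to be violated at entry. Every eligible subject therefore fails the composite at entry, q is 100%, and nothing is diluted.

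**6. Boundary values.** An SBP of 90, a heart rate of 90 or a respiratory rate of 20 is neither abnormal at entry nor stabilised later. Entry-normal subjects are thus not automatically counted as stabilised, so s need not be 100%.

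**The case against.** The strongest reply is that little hangs on this. The SAP's leading measure is the composite, which is unaffected. Both documents say that the intervals in this section are descriptive and that no non-inferiority conclusion will be drawn from them. The proportion of all randomised subjects within limits is a valid randomised comparison, and it also captures deterioration in subjects who were normal at entry. SAP 8.2 tabulates the baseline abnormalities by arm in ITT, so a reader will see each q. SAP 10.2 and 10.4 give changes from baseline in vital signs and laboratory grade shifts at the ECR visit. At q = 5% the restricted SBP row would hold about 17 subjects per arm.

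All of that stands, and it limits the point to labelling and one missing table. It does not remove it. The SAP 10.2 and 10.4 tables are in the Safety population, and 10.2 leaves out oximetry. None of the planned tables shows recovery of a vital sign among those in whom it was abnormal.

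A reader might also infer that Clinical Stability in Protocol 8.13.2 has the same fault, since "Patients will be considered clinically stable if they achieved all of the following criteria" can be satisfied before the first dose. Heart rate 95, respiratory rate 22, 37.0 °C, SBP 120, saturation 95% and white cells 13,000 meet criteria 4 and 5 and also all five stability limits. But that section names no denominator and describes a state on a given day, not recovery. The documents do not support calling it an error.

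**Conclusion.** The point holds for the per-sign rows in SAP 9.4. It holds for Protocol 12.8, clinical signs and laboratory findings included, to the extent that its items are reported singly. Those rows count never-abnormal subjects as stabilised and, if q and s are equal in the two arms, reduce a per-sign difference to q × D. For a 10-point difference that means 0.5 to 7.5 points as q runs from 5% to 75%; the values of q are assumptions.

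Three stronger readings are tempting and are not supported:

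- *False support for non-inferiority.* That conclusion rests on early clinical response in ITT, and none is drawn from this table. The primary analysis, sample size and alpha are unchanged.
- *The arms look alike whatever the drugs do.* At q = 75%, three quarters of the difference remains. Criterion 4 also means that the four signs cannot all have a low q.
- *Most subjects stabilised for blood pressure or oxygenation never had the abnormality.* This is plausible, since Protocol 6.3 excludes subjects who need drugs to support blood pressure or who need intensive care or ventilation. But the documents give no shares.

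This is a cheap improvement to a descriptive table.

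**What to change.** In SAP 9.4 and Protocol 12.8:

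- Keep the composite as it is.
- Keep the all-ITT per-sign rows, but label them 'within limits at 72–120 h'.
- For each sign or laboratory finding, add the rate among ITT subjects in whom it was abnormal at baseline by the criterion 4 or 5 limits. Alternatively, give a baseline by 72–120 h shift table by arm, which also shows subjects normal at baseline who became abnormal.
- Say where boundary values fall.
- Classify baseline status from pre-dose values. SAP 7.2 allows a vital sign taken up to 2 hours after the start of test article to serve as baseline; with pre-dose values the subset is defined before treatment and the comparison stays randomised.
- Optionally, show beside the Clinical Stability summary how many subjects already met its limits at Screening.

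The cost is SAP and protocol wording and some programming; the baseline values are already collected. The drawback is small denominators and imprecise percentages for rare signs such as SBP < 90 mmHg, where a shift table of counts may be more useful than a rate.

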6.1.4.1 Diagnosis of CABP

To be included in the CE-EOT and CE-PTE populations, subjects must meet the following protocol defined inclusion criteria that describe the CABP:

Inclusion Criterion 3: Has at least 3 of the following symptoms:

- Cough
- Production of purulent sputum
- Dyspnea (shortness of breath)
- Pleuritic chest pain.

Inclusion Criterion 4: Has at least 2 of the following abnormal vital signs:

- Fever or hypothermia documented by the investigator (po or rectal temperature > 38.0°C [100.4°F] or < 36.0°C [95.5°F])
- Hypotension with systolic blood pressure (SBP) < 90 mmHg
- Heart rate > 90 bpm
- Respiratory rate (RR) > 20 breaths/minute.

Inclusion Criterion 5: Has at least 1 clinical sign or laboratory finding associated with CABP:

- Hypoxemia Partial pressure of arterial oxygen (PaO₂) < 60 mmHg by arterial blood gas (ABG)
- Physical examination findings of pulmonary consolidation (dullness on percussion, bronchial breath sounds, egophony, rales, rhonchi, or decreased breath sounds)
- An elevated total white blood cell (WBC) count (> 12,000 cells/mm³) *or* leucopenia (WBC < 4,000 cells/mm³) *or* elevated immature neutrophils (> 15% band forms regardless of total peripheral WBC count).

Inclusion Criterion 6: Has disease categorized as being PORT III or IV at Screening

Inclusion Criterion 7: Radiographically-confirmed pneumonia, ie, new or progressive pulmonary infiltrate(s) on chest X-ray (CXR) or chest computed tomography (CT) scan consistent with acute bacterial pneumonia within 48 hours prior to the first dose of test article.

The Sponsor Medical Monitor will also review those subjects with a concomitant illness identified after baseline that could have presented at baseline as pneumonia, including COVID-19. If it is determined that the subject does not have pneumonia but had another condition such as lung cancer or COVID-19 at baseline, the subject will not be evaluable for the CE populations. Any subject who is confirmed or suspected to have severe acute respiratory syndrome coronavirus 2 (SARS-CoV-2) infection based on local standard-of-care assessments during the post-randomization period may be excluded from the CE populations based on Sponsor review.

6.1.4.2 **Prior Antibiotic Therapy**

Subjects will be excluded from the CE populations if they meet the prior antibiotic exclusion criteria:

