6.2 Evaluability Review Team

6.2.1 Membership and Responsibilities

The Evaluability Review Team (ERT) will review both clinical and microbiological data for determination of criteria used to assess inclusion in the analysis populations and for determination of baseline and post-baseline pathogens. ERT members will be blinded to treatment assignment and will review the data concurrent with the conduct of the study. The ERT will be conducted in accordance with the ERT Process Document.

6.2.2 **Process for Determining Inclusion in Populations**

Inclusion into the ITT and Safety populations will be determined programmatically from the eCRF data. Inclusion into the CE populations will be determined programmatically from the eCRF data and the manual review conducted by the ERT. The ERT may review subject data to confirm that population criteria are satisfied.

Inclusion into the microITT population will be determined programmatically by incorporating the outcome of the review of the isolates by the ERT. The ERT will determine whether each isolate (baseline and post-baseline) is considered a pathogen based on a review of information from baseline samples including Gram stain results, and local and central laboratory genus and species identification. Inclusion into the ME populations will be determined programmatically.

Review of data, Sponsor determination of evaluability, and final subject population classification will be performed in a blinded manner prior to database lock and unblinding with the exception of those criteria requiring the subject's actual treatment assignment (for example, the requirement for the subject to have received the correct test article per the randomization assignment). For the criteria requiring the subject's actual treatment assignment assignment, population determination will be completed programmatically.

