6.3 Subgroups

Analyses will be conducted (as described in Section 9) for subgroups defined by the randomization stratification factors: PORT Risk Class (III and IV) and receipt of an allowed antibacterial therapy in the 72 hours prior to study treatment (yes vs no). Analyses of ECR (in the ITT population) and clinical response at the PTE visit (in the ITT and CE-PTE populations) will also be conducted in the following subgroups: bacteremic subjects, defined as subjects with a positive blood culture at baseline (microITT population), by CURB-65 Score, and subjects meeting the systemic inflammatory response syndrome (SIRS) criteria at baseline. CURB-65 Score is derived from the eCRF data and ranges from 0-5 where 1 point is given for each of the following at baseline: confusion, blood urea nitrogen > 19 mg/dL (urea > 6.8 mmol/L), respiratory rate \geq 30 breaths/min, systolic blood pressure < 90 mmHg or diastolic blood pressure \leq 60 mmHg, and age \geq 65 years. Confusion is defined as altered mental status as recorded on the PORT Risk Class Determination eCRF. SIRS is defined as having 2 or more of the following criteria: temperature < 36°C or > 38°C (oral or oral equivalent), heart rate > 90 bpm, respiratory rate > 20 breaths/min, or WBC count < 4000 cells/mm³ or > 12,000 cells/mm³ or > 10% bands.

Exploratory analyses in other subgroups may also be conducted.

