Baseline assessments of clinical symptoms, clinical signs, abnormal vital signs, and abnormal laboratory signs of CABP will be presented for the ITT, Safety, microITT, and CE-PTE populations. The number and percentage of subjects with each of the CABP symptoms (cough, pleuritic chest pain, dyspnea, and phlegm/sputum production) by severity (absent, mild, moderate, severe) will be presented by treatment group. The number and percentage of subjects with the presence by severity (ie, absent, mild, moderate, severe) of the following clinical signs will be provided by treatment group: rales, rhonchi, dullness on percussion, bronchial breath sounds, wheezing, decreased breath sounds, and egophony. The number and percentage of subjects with fever (defined as body temperature > 38°C [100.4°F] oral or rectal), hypothermia (defined as body temperature < 36°C [95.5°F] oral or rectal), hypotension with systolic blood pressure < 90 mmHg, heart rate > 90 bpm, respiratory rate > 20 breaths/min, hypoxemia (defined as PaO₂ < 60 mmHg by arterial blood gas or

oxygen saturation < 90% by pulse oximetry), elevated total WBC count (> 12,000 cells/mm³), leucopenia (WBC < 4,000 cells/mm³), elevated immature neutrophils (> 15% band forms regardless of total peripheral WBC count) and any of elevated total WBC count, leucopenia or elevated immature neutrophils will be summarized by treatment group. Differences between treatment groups will be tested for statistical significance using Fisher's exact test.

Risk factors for CABP will be presented by treatment group for the ITT, Safety, microITT, and CE-PTE populations. Risk factors include smoking (current, past, and descriptive statistics of the number of years since quitting for those subjects who were previous smokers), receipt of pneumococcal vaccine, prior lung infection, whether the subject had mild to moderate COPD, symptomatic asthma with wheezing, and chronic cough with or without sputum production. Differences between treatment groups will be tested for statistical significance using Fisher's exact test for categorical variables and the Wilcoxon rank sum test for continuous variables. Other medical and surgical history will be summarized based on MedDRA system organ class by treatment group for the ITT and Safety populations.

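### The hypothermia limit in Inclusion 4, the CE rule and the baseline table is printed as two different temperatures: 36.0°C is 96.8°F, not 95.5°F

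*Protocol*

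**What the plan says.** Inclusion 4 in Protocol 6.2 reads "Has at least TWO of the following abnormal vital signs" and lists four: temperature, low systolic pressure, heart rate and respiratory rate. The temperature limits are "temperature > 38.0°C [100.4°F] or < 36.0°C [95.5°F", and the synopsis prints the same pair.

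The SAP uses the pair twice more:

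- **CE qualification (6.1.4.1).** The rule begins "To be included in the CE-EOT and CE-PTE populations, subjects must meet the following protocol defined inclusion criteria that describe the CABP", and its version of Inclusion 4 gives "po or rectal temperature > 38.0°C [100.4°F] or < 36.0°C [95.5°F". SAP 6.1.5 then builds the ME populations from the CE populations.
- **Baseline table (8.2).** The definition is "hypothermia (defined as body temperature < 36°C [95.5°F] oral or rectal".

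Other SAP definitions give Celsius only. SIRS in 6.3 uses "temperature < 36°C or > 38°C (oral or oral equivalent", and the modified ATS criteria (8.2) and the low-temperature flag in Table 9 (10.2) also use 36°C.

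The stabilisation summary at 72 to 120 hours (Protocol 12.8, SAP 9.4) asks for absence of fever and hypothermia without giving a number. Neither document says which unit governs or in which unit the eCRF stores temperature.

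**The concern.** A threshold given in two units should be one threshold. Here the Fahrenheit figure is a colder temperature than the Celsius figure, so the text contains two entry rules and does not rank them. Because Inclusion 4 needs two of four signs, temperature can be the deciding sign.

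Two things are at stake. At entry, two sites could both follow the printed text and reach opposite decisions on the same patient. In the analysis, the CE rule restates the same pair, so a programmer has to pick a limit. CE matters because Protocol 12.6.3 makes clinical response at the post-therapy evaluation (PTE) in the ITT and CE populations the EMA primary analysis and requires non-inferiority in both.

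**Working it through.** **Inputs.** The pair 36.0°C and 95.5°F (Protocol synopsis and 6.2; SAP 6.1.4.1 and 8.2). As controls, the other clinical temperature pairs: 38.0°C/100.4°F (Inclusion 4), 37.8°C/100°F (Protocol 7.6.5), and 35°C/95°F and 40°C/104°F (PORT worksheet, Protocol Appendix 5).

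**Formulae.** F = C × 9/5 + 32 and C = (F − 32) × 5/9.

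| Printed pair | Celsius converted | Agrees? |
|---|---|---|
| 38.0°C / 100.4°F | 38.0 × 9/5 + 32 = 100.4 | yes |
| 37.8°C / 100°F | 37.8 × 9/5 + 32 = 100.04 | yes, to rounding |
| 35°C / 95°F | 35 × 9/5 + 32 = 95.0 | yes |
| 40°C / 104°F | 40 × 9/5 + 32 = 104.0 | yes |
| 36.0°C / 95.5°F | 36.0 × 9/5 + 32 = 96.8 | **no** |

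**In reverse.** (95.5 − 32) × 5/9 = 63.5 × 5/9 = 35.28°C.

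**Size of the gap.** 96.8 − 95.5 = 1.3°F, or 36.0 − 35.28 = 0.72°C. Rounding cannot explain it: 35.95°C, the lowest value that rounds to 36.0°C, is 96.71°F. A fault in reading the PDF is also unlikely, since the same figure stands in four places across two documents and the fever pair beside it is exact.

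**Who is affected.** Readings from 95.5 to below 96.8°F. At 35.6°C (35.6 × 9/5 + 32 = 96.08°F) the reading is below 36.0°C but not below 95.5°F. Within the band, Inclusion 4 turns on the limit only when exactly one of the other three signs is abnormal. With two or three the criterion is met anyway; with none, temperature alone cannot reach two.

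**What each choice does to a patient in the band with exactly one other abnormal sign:**

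| Limit used at screening | Limit coded for CE | Result |
|---|---|---|
| 36.0°C | 36.0°C | eligible; meets the CE criterion |
| 36.0°C | 95.5°F | eligible; removed from CE and ME |
| 95.5°F | either | screen failure; never reaches ITT or CE |

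The error runs one way: everyone below 95.5°F is also below 36.0°C. In the second row the subject could count as hypothermic for SIRS and as not hypothermic for CE. The baseline count of hypothermia, and the stabilisation count if it takes its definition from there, change for any reading in the band, whatever the other signs.

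**The case against.** The conversion error itself is not open to dispute. The argument is over what follows from it, and several stronger readings fail.

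- **That CE membership depends on a site's thermometer.** A reader might infer this, but SAP 6.2.2 says "Inclusion into the CE populations will be determined programmatically from the eCRF data and the manual review conducted by the ERT". CE and the baseline table therefore turn on which limit is coded. A single rule in one unit, applied to converted data, removes any site dependence there. The direct link to a site's scale exists only at screening.
- **That sites in different regions apply different entry rules.** The text permits it, but nothing in the documents shows which scale any site uses.
- **That a count can be put on it, such as a few per cent of the 670.** The documents give no frequency for the band or for its combination with one other sign. Patients turned away at screening are also outside the 670.
- **That the primary result is biased.** The limit is a pre-randomization value applied alike to both arms of a double-blind trial. It does not enter the ECR definition, the margin, alpha or the power calculation. It can reach the ITT population only through who is enrolled.
- **That unqualified patients get in.** The bracketed value is the stricter one, so it can only turn away patients who meet the Celsius limit.

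Two further points stand. In this SAP (9.3) the intervals for clinical response at PTE in CE-PTE are descriptive; the EMA analysis, where CE is primary, has a separate SAP that is not among these documents. And definitions that differ by design, such as the 35°C limit in PORT, already classify subjects differently. That does not excuse a single definition with two values.

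**Conclusion.** The point holds as an error in an operative threshold. The two printed limits differ by 1.3°F (0.72°C). For patients in that band with exactly one other abnormal vital sign, the text does not settle eligibility, and it does not settle CE and ME membership until one limit is chosen for programming. The baseline hypothermia count is also unsettled for every subject in the band.

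The number affected is unknown and probably small, because two narrow conditions must coincide. That is a judgement; the documents give no data on it. The conclusion rests on both printed values being usable as written, since neither document ranks them. It does not call the ITT analysis method into question and does not imply a bias between arms. It is worth correcting because the rule governs entry and one EMA primary population, and because correcting it costs little.

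**What to change.** 1. Reconcile the Celsius and Fahrenheit values to one limit in the Protocol synopsis, Protocol 6.2, SAP 6.1.4.1 and SAP 8.2. The sponsor chooses the limit. The Celsius-only SAP definitions (SIRS, modified ATS, Table 9) use 36°C, which bears on consistency but does not settle the entry rule.
2. State in the SAP that this single limit is applied after unit conversion for CE membership, the baseline table and the stabilisation summary, which at present has no number. Carry the same limit into the separate EMA SAP.
3. Before database lock, run a blinded check of screening temperatures from 95.5 to below 96.8°F so that no subject is misclassified for CE. The listings of unmet entry criteria and of reasons for population exclusion already planned in SAP 8.1 cover part of this. If no subject falls in the band, record that.

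**Cost.** A minor protocol amendment or clarification, a SAP correction and a small amount of programming. Under Protocol 13.6.2 a protocol change needs a written amendment with sponsor and ethics approval, and health-authority approval where required, so the administrative step is more than retyping a figure. No added patients or procedures are needed.
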